### **7.9.2 Other Safety Evaluations**

Lip function, lip sensation, lip texture, lip firmness, lip symmetry and lip movement/function will be assessed prior to any injections and at all follow-up visits.

### **7.9.3 Definitions of Terms**

#### **7.9.3.1 Adverse Event**

An AE is defined as any untoward medical occurrence associated with the use of a drug/device in humans, whether or not considered drug/device-related (21 Code of Federal Regulations [CFR] 312.32 (a) and 803). An AE can therefore be any unfavorable and unintended sign (including an abnormal laboratory finding, for example), symptom, or disease temporally associated with the use of a drug/device, without any judgment about causality.

Expected adverse events are defined as the events that appeared at injection site subsequent to the first injection. Expected adverse events may include but are not limited to bruising, swelling, erythema, edema, inflammation at injection site.

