#### **7.9.3.3 Unexpected Adverse Event**

An AE or SAR is considered unexpected if it is not consistent with the risk information described in the labeling for the study devices.

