#### **7.9.6.3 Reference Safety Information for Assessing Expectedness of Adverse Events**

The reference safety information for assessing the expectedness of an AE for the study device in this study is the [PN40082 Instructions for Use](#) and the [Restylane® Silk Instructions for Use](#).

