### **7.9.7 Reporting Safety Observations**

Any SAE, whether deemed device-related or not, must be reported to the Sponsor or designee by telephone, email or fax as soon as possible after the investigator or coordinator has become aware of its

occurrence. The investigator/coordinator must complete a Serious Adverse Event (SAE) Form and email or fax it to the Sponsor or designee along with the subject's Adverse Events Log and Concomitant Medications Log within 24 hours of notification of the event. The Sponsor will notify the FDA of device-related SAEs.

Designee and Sponsor contact details:

[REDACTED]	[REDACTED]	[REDACTED]
[REDACTED]	[REDACTED]	Prollenium Medical Technologies, Inc. [REDACTED]

The investigator must be prepared to supply the medical monitor with the following information:

1. Investigator name and site number
2. Protocol number
3. Subject ID (screening/randomization) number
4. Subject initials and date of birth
5. Subject demographics
6. Clinical event
  - a. description
  - b. date of onset
  - c. severity
  - d. treatment (including hospitalization)
  - e. relationship to study device
  - f. action taken regarding study device
  - g. if the AE was fatal or life-threatening:
    - i. cause of death (whether or not the death was related to study device)
    - ii. autopsy findings (if available)

The Sponsor must submit a written summary of the clinical course of any life-threatening SAE and related subject information to the FDA within 7 days. Serious and unexpected AEs that are not life-threatening must be reported to the FDA within 15 calendar days. Any serious and unexpected AE

(including all deaths) must also be reported to the Institutional Review Board (IRB) by the investigator according to IRB reporting requirements and documentation of this report sent to the Sponsor or designee.

The investigator must provide a follow-up written report within 5 calendar days of reporting the event to the medical monitor. The written report must contain a full description of the event and any sequelae. Subjects who have had an SAE must be followed clinically until all parameters (including laboratory) have either returned to normal or are stabilized.

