### **9.2 Institutional Review Board (IRB)**

The study protocol and ICF must be approved in writing by an appropriate IRB as defined by FDA regulations and other applicable requirements prior to enrollment of any study subjects.

Any changes to the protocol or a change of investigator approved by the Sponsor must also be approved by the site's IRB and documentation of that approval provided to the Sponsor or designee. Records of the IRB review and approval of all documents pertaining to this study must be kept on file by the investigator and are subject to inspection by regulatory authorities during or after completion of the study. SAEs must also be reported to the IRB.

Periodic status reports must be submitted to the IRB at least annually, as well as notification of completion of the study and a final report within 1 month of study completion or termination. A copy of all reports submitted to the IRB must be sent to the Sponsor or designee.

The investigator will ensure that an IRB that complies with the requirements set forth in 21 CFR Part 56 will be responsible for the initial and continuing review and approval of the study.

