**WARNINGS**

- Defer use of *Restylane Silk* at specific sites in which an active inflammatory process (skin eruptions such as cysts, pimples, rashes, or hives) or infection is present until the process has been controlled.
- Injection site reactions (e.g., lip swelling, lip pain, and contusion) to *Restylane Silk* have been observed as consisting mainly of short-term minor or moderate inflammatory symptoms starting shortly after treatment, with an average of less than 18 days duration in the lips. In some cases delayed onset of these events has been observed with a range of 21 to 142 days after treatment. Most events with delayed onset resolved within 18 days. Injection site swelling appears to occur more frequently with the linear antegrade method of injection. Rare post-market *Restylane* reports of immediate post-injection reactions included extreme swelling of lips, the whole face and symptoms of hypersensitivity such as anaphylactic shock.
- Introduction of product into the vasculature may lead to embolization, occlusion of the vessels, ischemia, or infarction. Take extra care when injecting soft tissue fillers, for example inject the product slowly and apply the least amount of pressure necessary. Rare but serious adverse events associated with the *intravascular* injection of soft tissue fillers in the face have been reported and include temporary or permanent vision impairment, blindness, cerebral ischemia or cerebral hemorrhage, leading to stroke, skin necrosis, and damage to underlying facial structures. Immediately stop the injection if a patient exhibits any of the following symptoms, including changes in vision, signs of a stroke, blanching of the skin, or unusual pain during or shortly after the procedure. Patients should receive prompt medical attention and possibly

evaluation by an appropriate health care practitioner specialist should an intravascular injection occur.

- *Restylane Silk* must not be implanted into blood vessels. Localized superficial necrosis and scarring may occur after injection in or near vessels, such as in the lips, nose, or glabellar area. It is thought to result from the injury, obstruction, or compromise of blood vessels.
- Delayed onset inflammatory papules have been reported following the use of dermal fillers. Inflammatory papules that may occur rarely should be considered and treated as a soft tissue infection.

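### The protocol has two incompatible tests of expectedness and does not tie either label to its device, so some serious PN40082 events could miss the 15-day FDA report

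*Protocol*

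**What the plan says.** Protocol 7.9.3.1, within the definition of an adverse event, says: "Expected adverse events are defined as the events that appeared at injection site subsequent to the first injection". It then gives an open list: "Expected adverse events may include but are not limited to bruising, swelling, erythema, edema, inflammation at injection site". Nature, severity and seriousness play no part.

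Protocol 7.9.3.3 uses a different test: "An AE or SAR is considered unexpected if it is not consistent with the risk information described in the labeling for the study devices". The devices are in the plural and neither label is assigned to an arm. Section 7.9.6.3 begins "The reference safety information for assessing the expectedness of an AE for the study device in this study is the" and then names the PN40082 IFU and the Restylane Silk IFU together.

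Expectedness matters in 7.9.7. For the FDA: "Serious and unexpected AEs that are not life-threatening must be reported to the FDA within 15 calendar days". The same section has the investigator send serious and unexpected events, with all deaths included, to the IRB. Section 9.2 has no such filter: "SAEs must also be reported to the IRB".

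**The concern.** A reporting trigger should give one answer for one event. Here an injection-site event that is serious and outside the labeling is expected under 7.9.3.1 and unexpected under 7.9.3.3. Both stand under the same definitions heading, with no order of precedence.

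The second difficulty concerns the investigational product. Its IFU is the shorter of the two. The comparator's IFU carries marketed experience, including a long post-marketing list. If a PN40082 event may be checked against either label, experience with another product can make it expected.

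At stake is the timing of the FDA report and the trigger for one IRB report, for serious events on the device whose safety profile is least known.

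**Working it through.** No arithmetic applies. The check sets the sections side by side and follows an event through them.

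**Step 1. The labels compared.** The Post-Marketing Surveillance section of the Restylane Silk IFU names angioedema and abscess formation. The PN40082 IFU names neither. Its Precautions give a general risk of infection, and its Warnings name lip swelling as an injection-site reaction.

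**Step 2. Two serious, non-life-threatening PN40082 events under each test.**

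| Test | Injection-site abscess | Angioedema |
|---|---|---|
| 7.9.3.1 (location) | Expected | Expected if at the injection site; otherwise not addressed |
| 7.9.3.3 with the PN40082 IFU alone | Arguable: only general infection risk is given | Arguable: not named, though lip swelling is |
| 7.9.3.3 with both IFUs | Expected: named for Restylane Silk | Expected: named for Restylane Silk |

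The classification therefore depends on which sentence, and which IFU, the reader uses.

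**Step 3. Who decides, and with what information.** Section 7.6.1 gives the blinded Evaluating Investigator the recording of events, their severity and their relationship to device or procedure. It does not mention expectedness. Section 7.4.4 keeps assignments from the Sponsor staff who run the study. Section 7.9.10.2 allows an investigator to unblind only where treatment of the subject requires it, and the subject must then be withdrawn. No section says who judges expectedness or how that person would select an IFU.

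**Step 4. The reporting routes.** The last column takes an event that is serious but not fatal, life-threatening, embolic, ischemic or visual.

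| Route | Expectedness test? | Deadline | Reaches this event? |
|---|---|---|---|
| Any SAE to Sponsor (7.9.7) | No | Form within 24 hours of notification | Yes |
| Device-related SAE to FDA (7.9.7) | No | None stated | Yes, if judged related |
| Life-threatening SAE to FDA (7.9.7) | No | 7 days | No |
| Embolic, ischemic or visual event to FDA (7.9.3.4) | No | 10 working days | No |
| Serious, unexpected, not life-threatening, to FDA (7.9.7) | Yes | 15 calendar days | Only if called unexpected |
| Serious and unexpected, plus all deaths, to IRB (7.9.7) | Yes, except deaths | IRB's own requirements | Only if called unexpected |
| SAEs to IRB (9.2) | No | None stated | Yes |

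**Result.** For this class of event, the unsettled classification decides the 15-day FDA report and the 7.9.7 IRB report. Rows six and seven also disagree on which SAEs the IRB receives.

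**The case against.** The strongest reply is that 7.9.7 turns on the word unexpected, that 7.9.3.3 defines that word by labeling, and that 7.9.7 never refers to the location sentence. On the natural reading 7.9.3.3 governs. This has force. A reader might infer that every serious injection-site event is expected by definition, but that holds only if 7.9.3.1 overrides 7.9.3.3, which nothing says. What remains is that the protocol defines expected events in its definitions section, gives the term no other stated use there, and leaves the conflict open.

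Second, a reader might infer that the two IFUs form one pooled reference. The documents do not say so. Section 7.9.6.3 can equally mean that each device is judged against its own IFU. The supportable point is that the pooled reading is not excluded, and that masking makes it plausible because no process for choosing the IFU is described.

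Third, a reader might infer that grave events known from the comparator's label would go unreported on PN40082. The Restylane Silk IFU Warnings list events that "include temporary or permanent vision impairment, blindness, cerebral ischemia or cerebral hemorrhage". The visual, embolic and ischemic events among them go to the FDA under 7.9.3.4 whatever their expectedness. A life-threatening stroke or anaphylactic reaction goes within 7 days under 7.9.7. Such events do not show the gap. Nor does an event disappear from both FDA and IRB: 9.2 still sends SAEs to the IRB, and a device-related SAE is still notified to the FDA.

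Last, no efficacy endpoint is touched, and the safety summaries in Protocol 8.4 and SAP 5.6.1 do not use expectedness. That is correct.

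**Conclusion.** The point holds as a contradiction with a bounded effect on reporting. Sections 7.9.3.1 and 7.9.3.3 cannot both be applied. Sections 7.9.3.3 and 7.9.6.3 leave open which IFU applies to PN40082 and who decides under masking. Sections 7.9.7 and 9.2 disagree on the scope of IRB reporting.

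The exposure is confined to serious PN40082 events that are not fatal, life-threatening, embolic, ischemic or visual. For these, the possible loss is the 15-day FDA deadline and the 7.9.7 IRB trigger, so the risk is a late or disputed report and not complete silence. The documents give no basis for estimating how many events this would involve, so no frequency is offered.

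The conclusion assumes only that a site or Sponsor reader could reasonably follow the location sentence, or read the two IFUs together. The text permits both. The correction should be made, since it is cheap and concerns timely safety reporting on the investigational device.

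**What to change.** 1. In 7.9.3.1, delete the location sentence, or relabel it as a description of common injection-site reactions with no role in expectedness. The labeling test in 7.9.3.3 then stands alone.
2. In 7.9.3.3 and 7.9.6.3, state that a PN40082 event is not expected merely because the Restylane Silk IFU lists it.
3. State who judges expectedness and how, while assignment is masked. One option is to judge all masked SAEs against the PN40082 IFU. This needs no unblinding and, for the events compared above, errs toward reporting. Another is to judge each device against its own IFU, with a named function that may see assignment without unmasking the study team.
4. Reconcile 7.9.7 with 9.2 on which SAEs go to the IRB.

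The cost is a wording amendment to a few short sections. The first option in item 3 would also over-report some comparator events that are already in the Restylane Silk label. The second needs a described process and someone outside the masked team. Design, sample size and planned analyses are unchanged.

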#### **7.9.3.2 Suspected Adverse Reaction**

A suspected adverse reaction (SAR) is defined as any AE for which there is reasonable possibility that the drug/device caused the AE (21 CFR 312.32 (a)).

#### **7.9.3.3 Unexpected Adverse Event**

An AE or SAR is considered unexpected if it is not consistent with the risk information described in the labeling for the study devices.

#### **7.9.3.4 Adverse Events of Special Interest**

Certain events will require more detailed and timely reporting. These include:

- any changes in vision
- any events attributable to an embolic or ischemic cause (i.e., skin infarction)
- Any incidence of an event due to an embolic or ischemic cause or visual disturbances (including, but not limited to, any loss of vision, blurry vision, double vision, pain in or around eye, blind spot or shadow in the visual field, trouble moving eyes, etc.) MUST be immediately reported to the Medical Monitor by phone, email or fax. The investigator/coordinator must complete the AE source/CRF page and email or fax it to the Medical monitor as soon as possible after the investigator or coordinator has become aware of its occurrence. These reports will include the depth of injection, the injection volume, the symptoms that were observed, the time to onset, time

to resolution and any interventions that were implemented. The Sponsor will notify the FDA within 10 working days.

In the event of blindness or any ophthalmic signs or symptoms, subjects will undergo immediate evaluation by a retina specialist.

Refer to Appendix 1 for first aid protocol.

#### **7.9.3.5 Serious Adverse Event**

An SAE is defined as any AE or SAR that, in the view of the investigator or Sponsor, results in any of the following outcomes (21 CFR 312.32 (a)):

- Death
- Life-threatening AE (Note: the term “life-threatening” as used here refers to an event that in the view of the investigator or Sponsor places the subject at immediate risk of death at the time of the event; it does not include an AE or SAE that, had it occurred in a more severe form, might have caused death [21 CFR 312.32(a)])
- Inpatient hospitalization or prolongation of existing hospitalization. See exclusion to SAE reporting below under Planned Hospitalization.
- Persistent or significant incapacity or substantial disruption of the ability to conduct normal life functions
- Congenital anomaly/birth defect
- Required intervention to prevent permanent impairment/damage
- Any “other” important medical event. Important medical events that may not result in death, be life-threatening, or require hospitalization may be considered serious when, based upon appropriate medical judgment, they may jeopardize the subject and may require medical or surgical intervention to prevent one of the outcomes listed in this definition. Examples of such medical events include allergic bronchospasm requiring intensive treatment in an emergency room or at home, blood dyscrasias or convulsions that do not result in inpatient hospitalization, or the development of drug dependency or drug abuse.

#### **7.9.3.6 Planned Hospitalization**

A hospitalization planned by the subject prior to signing the ICF is considered a therapeutic intervention and not the result of a new SAE and should be recorded as medical history. If the planned hospitalization or procedure occurs as planned, the record in the subject’s medical history is considered complete. However, if the event/condition worsens during the study, it must be reported as an AE.

#### **7.9.4 Pregnancy**

Pregnancies occurring after administration of study device require immediate reporting. They must be reported within 24 hours after the investigator has become aware of the pregnancy. A pregnancy report will be completed and sent by fax to the Sponsor or designee within 24 hours of becoming aware of the pregnancy. The investigator will collect follow-up information regarding the outcome of the pregnancy and any postnatal sequelae in the infant that must also be reported to the Sponsor or designee. Upon awareness of the outcome of the pregnancy, the Principal Investigator or designee must forward a follow-up Pregnancy Report with any relevant information to the Sponsor or designee.

If the outcome of the pregnancy meets the criteria for immediate classification of an SAE (e.g., spontaneous abortion, stillbirth, neonatal death, or congenital anomaly), the investigator will report the

event by faxing a completed SAE report form to the Sponsor or designee within 24 hours of being notified of the pregnancy report.

The subject should immediately be withdrawn from the study.

### **7.9.5 Monitoring Adverse Events**

Each subject will be monitored for the occurrence of AEs, including SAEs, immediately after treatment initiation. Each subject will be followed for safety monitoring until discharged from this study. Follow-up procedures related to pregnancy or AEs or SAEs may continue beyond the end of the study.

Subjects will be questioned and/or examined by the investigator or a qualified designee for occurrence of AEs throughout the study. The presence or absence of specific AEs should not be elicited from subjects. In addition, subjects will be instructed to record AEs on the subject diary card during the 2 weeks after treatment. Subjects having AEs will be monitored with relevant clinical assessments and laboratory tests, as determined by the investigator.

AEs, actions taken as a result of AEs, and follow-up results must be recorded on the CRF, as well as in the subject's source documentation.

For all AEs that require the subject to be withdrawn from the study and SAEs, relevant clinical assessments will be repeated as clinically appropriate until final resolution or stabilization of the event(s).

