## 2 SCHEDULE OF ACTIVITIES

Visit Number (Month)	Visit 1 (Week 0)	Phone Contacts	Visit 2 (Mo 1)	Phone Contacts a	Visit 3 (Mo 2)	Visit 4 (Mo 3)	Phone Contacts	Visit 5 (Mo 6) End of Study/Early Termination	Unsched Visit
Scheduled Day(s)	Day 1	Day 3 & Day 14	Day 28	Day 33 & Day 44	Day 56	Day 84	Day 112 & Day 140	Day 168 b	
Scheduling Window	none	± 2 days	± 2 days	± 2 days	± 4 days	± 4 days	± 4 days	± 7 days	
Informed consent	X								
Medical history/ demographics	X								
Abbreviated Physical examination (including vital signs)	X								
Vision evaluations (Snellen visual acuity, confrontational visual fields, ocular motility) d	X		X		X	X	X	X	X c
Prior/Concomitant Medication/ Treatment	X	X	X	X	X	X	X	X	X
Inclusion/exclusion criteria review	X								
Urine pregnancy test e	X								
Fitzpatrick Skin Type	X								
Lip Fullness Grading Scale (LFGS) (Overall, upper lip and lower lip)	X		X		X	X		X	X c
Perioral lines at rest severity scale (POL) (Overall, upper lip and lower lip)	X		X		X	X		X	X c
Randomization	X								
Treatment with study device	X		X a						
Investigator Ease of Use Assessment	X		X a						
Evaluation for touch-up			X						
Patient GAI (pGAI)			X		X	X		X	X c
Swelling Assessment			X		X	X		X	X c
Investigator GAI (iGAI)			X		X	X		X	X c
Subject Satisfaction with Lips			X		X	X		X	X c
Lip Function (prior to injections)	X		X		X	X		X	X c
Lip Sensation (prior to injections)	X		X		X	X		X	X c
Lip Texture (prior to injections)	X		X		X	X		X	X c
Lip Firmness (prior to injections)	X		X		X	X		X	X c

Lip Symmetry (prior to injections)	X		X		X	X		X	X c
Lip Movement/Function	X		X		X	X		X	X c
Adverse event assessment	X	X	X	X	X	X	X	X	X
Treatment question								X	
Subject Diary	Dispense		Collect/ dispense f		Collect f				

Note: The timing of each visit is relative to Day 1, which is defined as the day the subject is randomized and first treated.

- a. For subjects who have touch-up treatment at Visit 2
- b. All subjects will receive a follow-up phone call at 12 months after first treatment.
- c. If/as needed
- d. performed prior to any treatment and repeated 30 minutes following any treatment and all follow-up visits.
- e. For women of childbearing potential, to be completed prior to enrollment.

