Safety will be assessed by monitoring adverse events (AEs) at all study visits. Adverse Events of Special Interest, any changes in vision and any events attributable to an embolic or ischemic cause (i.e., skin infarction) will be monitored. Other Safety evaluations include lip function, lip sensation, lip texture, lip firmness, lip symmetry, and lip movement/function. Other evaluations include Investigator Ease of Use Assessment, Swelling Assessment, and Subject Satisfaction with Lips Assessment.

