**7.7.2 Telephone Contacts on Day 3 and Day 14 ( $\pm$  2 days)**

- Assess AEs
- Assess concomitant medications/treatments
- Confirm adherence to prohibited treatments/medications

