Vascular compromise may occur due to an inadvertent intravascular injection or as a result of vascular compression associated with implantation of any injectable product. This may manifest as blanching, discoloration, necrosis or ulceration at the implant site or in the area supplied by the blood vessels affected; or rarely as ischemic events in other organs due to embolisation. Isolated rare cases of ischemic events affecting the eye leading to visual loss, and the brain resulting in cerebral infarction, following facial aesthetic treatments have been reported.

Vision abnormalities including blindness have been reported following injection of hyaluronic acid fillers into the nose, glabella, periorbital areas, and/or cheek, with a time to onset ranging from immediate to a few days following injection. Reported treatments include anticoagulant, epinephrine, aspirin, hyaluronidase, steroid treatment and hyperbaric oxygen. Outcomes ranged from resolved to ongoing at the time of last contact. Events requiring medical intervention, and events where resolution information is not available were reported. In these cases, the product was injected into the highly vascularized areas of the glabella, nose, and periorbital area, which are outside the device indications for use (See Warnings section).

Adverse reactions should be reported to Galderma Laboratories, L.P. at [name].

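### The rule against asking about specific adverse events makes no exception for vision and embolic/ischemic events, so between visits their detection rests on open-ended reporting; the schedule also marks eye examinations in a telephone column.

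*Protocol*

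**What the plan says.** Protocol 7.1 says that "any changes in vision and any events attributable to an embolic or ischemic cause (i.e., skin infarction) will be monitored". Section 7.9.3.4 names the same events as AESIs and says that they "MUST be immediately reported to the Medical Monitor by phone, email or fax".

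Section 7.9.5 sets the general method: "Subjects will be questioned and/or examined by the investigator or a qualified designee for occurrence of AEs throughout the study". It then adds: "The presence or absence of specific AEs should not be elicited from subjects". Neither 7.9.5 nor 7.9.3.4 says that AESIs are handled differently.

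The calls on Days 3 and 14 (7.7.2) and, after a touch-up, on Days 33 and 44 (7.7.4) have three items: assess AEs, review concomitant medications and treatments, and "Confirm adherence to prohibited treatments/medications". The Day 112 and Day 140 calls (7.7.6) have the same three. None mentions vision or ischemic symptoms.

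Section 7.6.6 has a trained evaluator perform the eye examinations before treatment, 30 minutes after it and at follow-up visits. In the schedule (Protocol Section 2, repeated in SAP 7.2), the row "Vision evaluations (Snellen visual acuity, confrontational visual fields, ocular motility" also carries an X in the Day 112/140 telephone column.

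**The concern.** A rule against prompting is a reasonable convention for general AE collection because it avoids suggestion. It fits poorly with a short list of named events that the protocol singles out for monitoring and immediate reporting. Staff who follow 7.9.5 as written have no instruction to ask about eye symptoms or signs of ischemia on the calls, and some reason not to.

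These events carry weight. Protocol 7.9.9 ties site and study suspension to embolic events with skin necrosis, vision loss or stroke. Protocol 8.4 summarizes visual events separately, and the SAP gives vascular and visual events their own table series (14.3.2.x). If ascertainment is incomplete, low counts in those tables are harder to interpret.

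The mark in the telephone column is a separate matter. Those three tests, done by a trained evaluator, do not fit a telephone contact, and the text does not ask for them there.

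**Working it through.** The plan gives no figure on this point. The check is of intervals and of text against text.

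**Interval between eye examinations, first treatment.** Last examination: Day 1, 30 minutes after injection (7.6.6, 7.7.1). Next: Visit 2, Day 28 ± 2, so Day 26 to 30.
- Shortest: 26 − 1 = 25 days.
- Longest: 30 − 1 = 29 days.

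**Interval after a touch-up.** The touch-up is at Visit 2, Day 26 to 30. Next examination: Visit 3, Day 56 ± 4, so Day 52 to 60.
- Shortest: 52 − 30 = 22 days.
- Longest: 60 − 26 = 34 days.

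**What covers those intervals.**
- Two calls in each: Day 3 ± 2 (Days 1 to 5) and Day 14 ± 2 (Days 12 to 16); after a touch-up, Day 33 ± 2 (Days 31 to 35) and Day 44 ± 2 (Days 42 to 46). All carry a general AE item only.
- A diary for two weeks after each treatment (7.6.24), open to any AE. It is reviewed when returned (7.9.8), and the first one is collected at Visit 2. A symptom written down on Day 3 could wait 26 − 3 = 23 to 30 − 3 = 27 days to be read, unless the subject also reports it by another route.
- Subject-initiated contact: unscheduled visits are allowed at any time and may include the eye examination (7.7.8), and subjects are given ophthalmology and emergency contacts (Appendix 1).

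None of these puts a direct question about an AESI to the subject.

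**Timing of onset.** The post-marketing section of the comparator's instructions describes vision abnormalities "with a time to onset ranging from immediate to a few days following injection". That describes injections into the nose, glabella, periorbital areas and cheek, not the lips. Appendix 1 describes the visual symptoms as usually immediate. The 30-minute examination covers immediate onset. The Day 3 call is the only scheduled contact aimed at the following few days.

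**Schedule mark.** The table has nine columns: Visit 1, calls, Visit 2, calls, Visit 3, Visit 4, calls, Visit 5, unscheduled. The vision row reads X, blank, X, blank, X, X, X, X, X (if needed). The seventh cell is the Day 112/140 calls. The lip fullness row has the same nine cells and is blank there. The SAP copy shows the same pattern, so a table-reading fault is unlikely. Against it stand 7.6.6 and schedule footnote d, which tie the examinations to treatments and follow-up visits, and 7.7.6, which does not list them.

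**The case against.** The strongest reply is that 7.9.5 is a recommendation, not a prohibition, and stands directly after a requirement to question or examine subjects for AEs throughout the study. Non-leading questioning is a recognized choice. Loss of vision, double vision, eye pain and skin infarction are hard to overlook, and a subject asked an open question on Day 3 would probably mention them. An objective eye examination follows every injection at 30 minutes, when onset is said to be most usual, and is repeated at every visit. The diary, unscheduled visits and emergency contacts add further routes.

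Most of this stands. It rules out a stronger reading that a reader might infer: that the calls cannot ask about vision at all, and that early events will be missed. The text does not say either. It does not remove the narrower point, because every route between visits is open-ended, retrospective or dependent on the subject, and staff are given no exception for events the protocol ranks as urgent.

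A reader might also infer that Month 4 and 5 vision data will be missing for every subject. The documents do not show this: sites may simply follow 7.7.6, and the examinations feed a listing (16.2.4.7) rather than a tabulated analysis. Nor does an upper confidence limit for zero events in 79 subjects per arm measure the problem. That limit depends on sample size and is the same whether or not subjects are prompted.

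**Conclusion.** The point holds as a gap in ascertainment. For 25 to 29 days after first treatment and 22 to 34 days after a touch-up, the plan relies on open-ended reporting for the events it most wants to detect, and the general rule in 7.9.5 is not reconciled with 7.1 and 7.9.3.4. Less conspicuous or transient AESIs may be under-reported or reported late. How many cannot be estimated from the documents, and nothing suggests that the effect would differ between arms.

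This rests on two assumptions: that sites apply 7.9.5 to AESIs as to any other AE, and that the call content is no more than the visit-specific lists show. A call script outside these documents that already asks about vision would largely answer the point.

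The telephone-column X is a genuine inconsistency in both documents, but a clerical one to be reconciled, not a demonstrated loss of data.

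**What to change.** 1. In Protocol 7.9.5, exempt the AESIs of 7.9.3.4 from the rule against eliciting specific events.
2. Add to the calls in 7.7.2, 7.7.4 and 7.7.6 a fixed question, put after the open AE question, identical in both arms and asked by blinded staff. Use the list of visual symptoms already in 7.9.3.4.
3. Word any ischemia item to separate it from expected bruising and redness. A general question on skin color would be of little use: in the comparator's pivotal study, diary bruising was reported by 81% and redness by 70% after first treatment (Restylane Silk instructions, Table 2).
4. Flag these reports as solicited in the AE data and tabulate them separately. The SAP's AE listings already carry a reporting-source column that could hold the flag.
5. Reconcile the vision-evaluation X in the Day 112/140 column of Protocol Section 2 and SAP 7.2 with Protocol 7.6.6 and 7.7.6.

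The cost is protocol and SAP wording, a short call script and CRF fields. The downside is some additional low-specificity reports in both arms, which the flag keeps separable. The interval between eye examinations does not change; the fix adds a direct question within it.
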